Pregnancy Test ^h	X	X	X	X	X	X	X		X
FSH ⁱ	X								
ABO and Rh Blood Type ^j	X								
Serum Chemistry ^k	X	X	X	X	X	X	X		X
Hematology, differential, reticulocytes ^l	X	X	X	X	X	X	X	X ^u	X
T/B/NK counts ^r		X	X		X				
PT/INR, aPTT ^m	X	X	X	X	X	X	X		
TPO levels ^r		X	X	X	X	X	X		
Hemolysis panel ^{n, r}		X	X	X	X	X	X		
Immunoglobulin Levels ^r		X	X		X				
PK sample ^o		X			X				X
BTK Occupancy (at select sites) ^{p, r}		X			X				
(Optional) sample for vaccine-specific IgG ^{r, s}		←=====→							X
QOL Questionnaires ^q	X	X	X	X	X	X	X		X
IBLS	X	X	X	X	X	X	X		X
Rilzabrutinib or Placebo dispensed		X	X	X	X	X	X		
Patient Medication Diary		X	X	X	X	X	X		
SARS-CoV-2 test	X ^{u, v}	X ^r							

AE = adverse event; aPTT = activated partial thromboplastin time; BTK = Bruton's tyrosine kinase; D = day; ECG = electrocardiogram; EQ-5D-5L = EuroQOL-5 Dimension 5 Level; FSH = follicle-stimulating hormone; HBV = hepatitis B virus; HBsAg = hepatitis B surface antigen; Hep = hepatitis; HIV = human immunodeficiency virus; IBLS = ITP Bleeding Scale; IgG = immunoglobulin G; INR = international normalized level; IMP = investigational medicinal product; ITP = immune thrombocytopenia; ITP-PAQ = ITP- Patient Assessment Questionnaire; ITP- KIT = Kids' ITP Tools; PGIC = Patient Global Impression of Change; PGIS = Patient Global Impression of Severity; PGIS-Fatigue = Patient Global Impression of [Fatigue] Severity; PK = pharmacokinetics; PT = Prothrombin time; QOL = Quality of Life; Rh = rhesus factor; SARS-CoV-2 = severe acute respiratory syndrome-related coronavirus-2; SD = study day; TB = tuberculosis; T/B/NK = T-lymphocytes/B-lymphocytes/natural killers; TPO = Thrombopoietin; WK = Week.

- a Participants may be re-screened once. The screening period can be up to -31 days of Study Day 1.

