- l QOL Questionnaires include EQ-5D-5L, ITP-PAQ or ITP-KIT, and PGIS-Fatigue/PGIS/PGIC. ITP-PAQ, EQ-5D-5L and PGIS-Fatigue/PGIS/PGIC (in that order) will be administered for adults 18 years or older. ITP-KIT and EQ-5D-5L (in that order) will be administered for pediatric participants (see [Appendix 10.7](#) for EU [EEA countries] age ranges). **Questionnaires should be completed prior to all other study procedures and interactions with site staff.**
- m See [Appendix 10](#) for country-specific requirements.
- n Optional collection of 2 blood samples for vaccine-specific IgG in serum (see [Section 7.9.9](#) for a list of routine vaccines). The first blood sample should be collected within 6 weeks prior to each vaccine dose regimen and the second blood sample should be collected within approximately 3 to 6 weeks after the vaccine dose regimen is complete. Whenever possible, blood for vaccine-specific IgG should be collected at a scheduled visit; but may also be collected during an Unscheduled Visit. Dates of vaccination, disease, brand name of vaccine product and antigenic strain should be recorded.
- o Week 25/SD169 visit is the last visit of the blinded treatment period and may also serve as the start of the open label period.
- p For participants who will enter the open label period directly after 12 weeks of blinded treatment, they will attend the Week 13/SD85 visit which corresponds to the Week 25/SD169 visit (Table 2), this would be their last visit of the blinded treatment period and also the start of the open label period. They will follow the open label period schedule of assessments from Week 29 (Table 2) starting at their next scheduled visit for a total of 28 weeks.
- q For participants who will enter the open label period directly after 12 weeks of blinded treatment, they will follow the open label period schedule of assessments (**Week 25 to Week 53**) which means that they will be treated on the open-label part for a total of 28 weeks. After Week 53, the participants will follow the schedule of assessments according to their eligibility for the LTE period.

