4.1.2. Blinded Treatment Period (Weeks 1 to 25)

Day 1 Week 1:

- Verify participant still meets Inclusion/Exclusion criteria (use screening lab results for eligibility determination) and randomize eligible participants to treatment
- Complete ITP-PAQ or ITP-KIT, EQ-5D-5L, and PGIS-Fatigue/PGIS/PGIC patient questionnaires
- Record concomitant medications
- Record AEs
- Record weight (kg)
- Conduct abbreviated physical examination; See [Appendix 10.6](#) for Italy-specific requirements
- Complete IBLs
- Capture vital signs (body temperature, respiratory rate, blood pressure, and pulse rate)
- Collect 12-lead single ECG
- Collect urine sample for urinalysis
- Conduct urine pregnancy test (women of childbearing potential)
- Collect clinical laboratory blood samples:
 - Hematology (hemoglobin, hematocrit, RBCs, platelets, mean platelet volume, WBCs with differentials [neutrophils, eosinophils, basophils, lymphocytes, and monocytes])

- Serum chemistry (AST, ALT, bilirubin, ALP, albumin, creatinine, urea, total protein, sodium, chloride, calcium, phosphate, potassium, and glucose [random])
- Coagulation (PT/INR, thrombin time, aPTT, fibrinogen level)
- Collect PK blood samples
- Collect exploratory laboratory blood samples (see [Appendix 10](#) for country-specific requirements):
 - T/B/NK counts
 - TPO levels
 - Hemolysis panel
 - Immunoglobulin levels
 - BTK occupancy (at select sites)
 - (Optional) vaccine-specific IgG response
- Dispense rilzabrutinib or placebo
- For country-specific requirements please refer to [Appendix 10](#).

Week 5:

- Complete ITP-PAQ or ITP-KIT, EQ-5D-5L and PGIS-Fatigue/PGIS/PGIC patient questionnaires
- Record concomitant medications
- Record AEs
- Record weight (kg)
- Conduct abbreviated physical examination
- Complete IBLs
- Capture vital signs (body temperature, respiratory rate, blood pressure, and pulse rate)
- Collect urine sample for urinalysis
- Conduct urine pregnancy test (women of childbearing potential)
- Collect clinical laboratory blood samples:
 - Hematology (hemoglobin, hematocrit, RBCs, platelets, mean platelet volume, WBCs with differentials [neutrophils, eosinophils, basophils, lymphocytes, and monocytes])
 - Serum chemistry (AST, ALT, bilirubin, ALP, albumin, creatinine, urea, total protein, sodium, chloride, calcium, phosphate, potassium, and glucose [random])
 - Coagulation (PT/INR, thrombin time, aPTT, fibrinogen level)

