5. ELIGIBILITY CRITERIA

5.1. Inclusion Criteria

Participants may be included in the study if ALL of the following criteria are met:

1. Participants will be male and female with primary ITP with duration of >6 months in pediatric participants aged 12 to <18 years (pediatric participants aged 10 to <12 years will be enrolled in the EU [EEA countries] only; refer to [Appendix 10.2](#), [Appendix 10.3](#), and [Appendix 10.7](#) for country-specific requirements) and duration of >3 months in adults aged ≥ 18 years
2. Participants who had a response (achievement of platelet count $\geq 50,000/\mu\text{L}$) to IVIg/anti-D or CSs that was not sustained and who have documented intolerance, insufficient response, or any contraindication to any appropriate courses of standard of care ITP therapy
3. An average of 2 platelet counts at least 5 days apart of $<30,000/\mu\text{L}$ during the screening period and no single platelet count $>35,000/\mu\text{L}$, within 14 days prior to the first dose of study drug
 - Pediatric participants must additionally be determined to need treatment for ITP as per clinical assessment by the Investigator (see [Appendix 10.7](#) for EU [EEA countries] specific criteria)
4. Adequate hematologic, hepatic, and renal function (absolute neutrophil count $\geq 1.5 \times 10^9/\text{L}$, AST/ALT $\leq 1.5 \times$ upper limit of normal (ULN), albumin ≥ 3 g/dL, total bilirubin $\leq 1.5 \times$ ULN [unless the participant has documented Gilbert syndrome], estimated glomerular filtration rate (GFR) >50 [Cockcroft and Gault method for adult and Bedside Schwartz Equation for Pediatric participants])
5. Hemoglobin >9 g/dL within 1 week prior to Study Day 1
6. All contraceptive use by men and women should be consistent with local regulations regarding the methods of contraception for those participating in clinical studies.

A) Male participants

Male participants are eligible to participate if they agree to the following during the intervention period and for at least 13 weeks after the last administration of study intervention:

- Refrain from donating or cryopreserving sperm
- Plus, either:
- Be abstinent from heterosexual intercourse as their preferred and usual lifestyle (abstinent on a long term and persistent basis) and agree to remain abstinent
- OR
- Must agree to use contraception/barrier as detailed below

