## 3 STATISTICAL ANALYSES

### 3.1 GENERAL CONSIDERATIONS

In general, continuous data will be summarized using the number of observations available, mean, standard deviation (SD), median, (Q1 and Q3 as needed), minimum, and maximum. Categorical and ordinal data will be summarized using the count and percentage of participants.

The baseline value is defined as the last available value before the first dose of double-blind investigational medicinal product (IMP). For participants randomized but not treated, the baseline value is defined as the last available value before randomization.

The baseline value of platelet count is defined as the average of a patient's three platelet counts before the first dose of double-blind IMP: the two qualifying platelet counts at screening collected in eCRF and the platelet count at Week 1 (Study day 1).

Note: Platelet counts conducted locally will be used for efficacy analyses. Platelet counts conducted centrally will be used as a back-up for missed or non-analyzable local lab samples.

Unless otherwise specified,

- Analyses will be performed separately for adult and pediatric populations.
- Analyses will be performed by intervention group (and overall for baseline and demographics characteristics) during the double-blind period.
- Analyses will be performed in the participants who have been exposed to rilzabrutinib during each respective period for OL and LTE. Please refer to [Section 2](#), [Section 3.6](#), [Section 3.6.2](#), [Section 3.6.3](#).
- Cumulative safety analyses across periods will be based on rilzabrutinib safety population. Please refer to [Section 2](#), [Section 3.6](#), [Section 3.6.2](#), [Section 3.6.3](#).
- Limited analyses will be provided during the initial 12 weeks of double-blind treatment period before participants cross over to open-label period to have a full safety profile (see [Table 7](#)).

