### ***Observation period***

The observation period will be divided into 3 segments:

- The **pre-treatment period** is defined as the period up to first double-blind IMP administration.
- **Double-blinded (DB) period**
  - The DB on-treatment period is defined as the period from the first DB IMP administration to the last DB IMP administration + 1 day for participants who did not enter the OL period or to the first OL IMP (the first OL visit is the nominal protocol visit Week 25) for participants who entered the OL period.
  - The DB post-treatment period is defined as the period after the DB on-treatment period for participants who did not enter the OL period.
- **Open-Label (OL) period**
  - The OL on-treatment period is defined as the period from the end of the DB on-treatment period to the last OL IMP administration + 1 day for participants who did not enter the LTE period or to the first OL IMP during the LTE (the first LTE visit is the nominal protocol visit Week 53) for participants who entered the LTE period.
  - The OL post-treatment period is defined as the period after the OL on-treatment period for participants who did not enter the LTE period.
- **Long-term extension (LTE)**
  - The LTE on-treatment period is defined as the period from the end of OL on-treatment period to the last IMP administration + 1 day.

- The LTE post-treatment period is defined as the period after the LTE on-treatment period to the end of study.

Note: Per protocol, the end of study visit occurs 4 weeks post last dose of IMP during the DB, OL or LTE period, whichever later.

Events occurred after the first double-blind IMP administration are considered treatment emergent, including on- and post-treatment events, as defined above. That is, **double-blind treatment-emergent period** includes double-blind on- and post-treatment period. **Open label treatment-emergent period** and **LTE treatment-emergent period** are defined similarly. For rilzabrutinib safety population, the entire treatment-emergent period will start from the 1st administration of rilzabrutinib.

For safety analysis, the 12-week double-blind treatment emergent period is the double-blind treatment emergent period for those discontinued before Week 13 (Day 85) or the period from the first double-blinded IMP administration to the visit date of Week 13 otherwise.

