#### ***Additional analyses for drug-induced liver injury***

The following additional analyses will be performed for drug-induced liver injury:

- Time to onset of the initial ALT or AST elevation ( $>3 \times \text{ULN}$ ) and total bilirubin elevation ( $>2 \times \text{ULN}$ ) (time to first observation of ALT or AST elevation or total bilirubin elevation, whichever comes first) during the treatment-emergent period will be analyzed using Kaplan-Meier method.
- A graph of the distribution of peak values of ALT versus peak values of total bilirubin during the treatment-emergent period will be provided.
- For each liver function test (eg, ALT), participants having experienced a PCSA (eg, ALT  $>5 \text{ ULN}$ ) will be summarized using the following categories (for each treatment period or cumulatively as appropriate): Returned to baseline PCSA status (or returned to value  $\leq \text{ULN}$  in case of missing baseline) before last IMP dose, Returned to baseline PCSA status after last IMP dose, Never returned to baseline PCSA status (or not yet returned to baseline PCSA status at the data cutoff if applicable), No assessment after elevation. This summary will be performed by categories of elevation (ALT  $>3$ ,  $>5$ ,  $>10$ ,  $>20 \text{ ULN}$ ).

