**Table 9 - Analyses of laboratory variables, vital signs and electrocardiograms**

		DB 24W		OL a	LTE b	DB+OL+LTE c
		Adults	Pediatrics	Adults and Peds Separately		
Laboratory, vital signs, ECG	Descriptive summary d	✓	✓	✓	✓	
	Overtime (by-visit) plot d	✓	✓	✓	✓	
	PCSA (or PCSA-like) shift summary	✓	✓	✓	✓ d	✓ d
DILI	Time to first onset	✓	✓	✓		
	Plot of peak values of ALT versus peak values of total bilirubin	✓	✓	✓		✓
	Return to baseline PCSA status summary	✓	✓	✓		✓

a Cumulative data from 1st dose of rilzabrutinib during OL period. Adult and pediatric populations separately.

b Cumulative data from 1st dose of rilzabrutinib during LTE period. Adult and pediatric populations separately.

c Cumulative data from 1st dose of rilzabrutinib regardless of period. Adult and pediatric populations separately.

d For selected laboratory tests only.

DB = double-blind period; OL = open-label period; LTE = long-term extension; 24W = 24-week double-blind period;

DILI = drug-induced liver injury; ECG = electrocardiograms; PCSA = Potentially Clinically Significant Abnormalities; ALT = alanine aminotransferase.

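### The liver time-to-onset curve has no baseline condition, so a bilirubin already above 2 x ULN in Gilbert syndrome can be dated as a new liver onset

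*SAP*

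**What the plan says.** - **Event.** SAP 3.6.3.1 plans a Kaplan-Meier analysis of time to onset of ALT/AST above 3 x ULN and total bilirubin above 2 x ULN in the treatment-emergent period. The lead-in joins the two components with *and*, but the bracket that follows defines the event as "time to first observation of ALT or AST elevation or total bilirubin elevation, whichever comes first". One component is therefore enough. No baseline status or at-risk set is given.
- **Treatment-emergent.** SAP 3.1 defines this by time alone: "Events occurred after the first double-blind IMP administration are considered treatment emergent".
- **Entry limits.** Protocol 5.1, criterion 4, requires AST/ALT at or below 1.5 x ULN without exception. Total bilirubin must also be at or below 1.5 x ULN, "unless the participant has documented Gilbert syndrome". No alternative ceiling is set for those participants.
- **Which sample decides eligibility.** On Day 1 the site is told: "Verify participant still meets Inclusion/Exclusion criteria (use screening lab results for eligibility determination". Protocol Table 1, footnote a, adds: "The screening period can be up to -31 days of Study Day 1".
- **Baseline.** SAP 3.1: "The baseline value is defined as the last available value before the first dose of double-blind investigational medicinal product (IMP").
- **Open label.** SAP Table 9 also ticks time to first onset for the open-label period, with the footnote "Cumulative data from 1st dose of rilzabrutinib during OL period". For participants who move at Week 13, Protocol Table 2, footnote p, says of that visit that "this would be their last visit of the blinded treatment period and also the start of the open label period".

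**The concern.** A curve labelled time to onset should show when new abnormalities appear on treatment. As written, this one records the first post-dose value above a threshold, whether or not the value was above it beforehand. A participant with Gilbert syndrome who enters with bilirubin above 2 x ULN has an event at the first post-dose chemistry (Week 5 in the schedule) if the value is still raised. Because the event is a composite first event, that participant then leaves the risk set, and a later ALT/AST rise does not enter the curve.

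The neighbouring outputs do take baseline into account. Incidence of potentially clinically significant abnormalities (PCSA) is given both overall and by baseline status, and the recovery summary is relative to baseline PCSA status. Protocol 2.7.1 lists liver enzyme elevation as an important potential risk, and none of the planned outputs gives a time to new ALT/AST elevation free of pre-existing values.

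**Working it through.** The plan states no figure for this curve, so there is none to reproduce. The check sets event thresholds against entry limits, looks at what else would show the signal, and then sizes the effect.

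**1. Can a pre-dose value already be above the event threshold?**

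| Component | Limit at screening | Event threshold | Rise needed from the limit |
|---|---|---|---|
| ALT/AST, all participants | 1.5 x ULN | >3 x ULN | more than 3/1.5 = 2-fold |
| Bilirubin, no Gilbert syndrome | 1.5 x ULN | >2 x ULN | more than 2/1.5 = 1.33-fold |
| Bilirubin, documented Gilbert syndrome | none | >2 x ULN | none |

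The open route is bilirubin in Gilbert syndrome. For ALT/AST two narrow routes remain:
- A more than two-fold rise between screening and Day 1, in a window of at most 31 days. The Day 1 check relies on screening results, so such a value would not bar dosing.
- An elevation carried into open label, where the clock starts at the first open-label dose. The SAP baseline precedes double-blind dosing, so it does not identify this case.

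**2. What else shows a later rise in the other component?**
- PCSA incidence by baseline status (SAP 3.6.3.1).
- The combined criterion, ALT >3 x ULN with bilirubin >2 x ULN, counted within a treatment phase at any interval (SAP 5.6.1).
- The plot of peak ALT against peak bilirubin, which does not stop at a first event (SAP 3.6.3.1).
- ALT >3 x ULN as an adverse event of special interest (Protocol 9.3.9.6).

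A later rise is therefore lost from this curve only.

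**3. Size.** Inputs are 129 and 65 adults (SAP 4), taking all randomized as treated. The number affected, g, is not in the documents. I assume 0 to 3, all still above threshold at the first post-dose sample.

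Increase in the early onset proportion if all g are in one arm, g/n:
- Rilzabrutinib: 1/129 = 0.78 points; 3/129 = 2.33 points.
- Placebo: 1/65 = 1.54 points; 3/65 = 4.62 points.
- g = 0: nil.

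The increase lasts to the end of the curve only if the participant would otherwise have had no event.

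Difference between arms: randomization makes its expectation zero. With X the number of the g affected who fall in the rilzabrutinib arm (hypergeometric), the chance SD is

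sqrt(g x 0.665 x 0.335 x (194 - g)/193) x (1/129 + 1/65)

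which gives 1.09 points for g = 1, 1.54 for g = 2 and 1.88 for g = 3.

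Planned pediatric arms: 1/20 = 5 points on rilzabrutinib; 1/10 = 10 points on placebo. The open-label denominator is not given.

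**The case against.** The strongest reply is that the words *onset* and *initial*, with a treatment-emergent rule about events occurring after first dosing, already imply a new abnormality: a value raised on Day 1 did not begin after dosing. That is a fair reading of intent. It does not settle the matter, because the bracket makes the event the first observation above threshold, and that is what would be programmed. What stands is that this is a clarification of wording rather than an error that changes a conclusion.

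The reply also has these points:
- Leaving the risk set at the first component is how any composite first event works. True; the fault lies in letting a pre-existing value be that event.
- Separate curves lose the single time to first liver abnormality. Also true, and a matter of preference.
- No document reports an enrolled participant with Gilbert syndrome. Correct, so the number affected may be zero.

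A reader might infer that ALT/AST is as exposed as bilirubin, since no baseline condition is stated for either. The documents do not support that. The ALT/AST limit is half the event threshold and has no exception. Both remaining ALT/AST routes are narrow, and the open-label one is further limited for ALT: values above 3 x ULN must be retested within 72 hours (Protocol 9.3.9.6), and treatment must stop when the Appendix 15 conditions are met (Protocol 7.5.1). Those ALT rules do not cover AST, and the Appendix 15 decision figure was not available for this check, so carry-over is limited but not excluded.

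**Conclusion.** The point holds, chiefly for bilirubin. Followed as written, the rule can date a pre-existing bilirubin above 2 x ULN in documented Gilbert syndrome as a new liver onset and remove that participant before any ALT/AST rise. Each such adult adds 0.8 points to the early onset proportion on rilzabrutinib or 1.5 on placebo, with no expected difference between arms. This assumes that the value is still above threshold at the first post-dose sample and that all randomized adults are treated. The range of 0 to 3 affected adults is an assumption.

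A reader might go further and infer that a hepatocellular or Hy's Law signal could be hidden, or that the treatment comparison is biased. Neither follows. The PCSA tables, combined criterion, special-interest events and peak plot still carry the signal. SAP 3.6 plans no safety testing, and nothing in the primary or key secondary analyses depends on this curve. It is a cheap improvement.

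**What to change.** In SAP 3.6.3.1, replace the composite with two Kaplan-Meier curves, one for ALT or AST above 3 x ULN and one for total bilirubin above 2 x ULN. In each, count an event only in participants at or below that component's threshold at the last value before the first double-blind dose. A participant with Gilbert syndrome and raised bilirubin then stays at risk in the ALT/AST curve. Keep everyone in the PCSA tables, the combined criterion and the peak plot. This also removes the *and*/*or* conflict in the current text.

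For open label, flag elevations already present at the first open-label dose as carried over instead of dating them as new. Do not simply reset the baseline at that visit and exclude whoever is raised: that would drop elevations that arose on double-blind rilzabrutinib, which should stay visible in the open-label output.

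The cost is SAP wording and one extra descriptive curve per display. ALT, AST and bilirubin are already collected at screening, on Day 1 and at the visit that starts open label, so no new data are needed. The downside is that participants above a threshold at baseline are omitted from that one component's curve.
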